## **1. PURPOSE OF THE ANALYSES**

The statistical analysis plan (SAP) is being developed after review of the AzurRx BioPharma, Inc. (AzurRx), protocol number AZ-CF2002, but before any analyses of the data. The SAP contains detailed information to aid in the implementation of the statistical analyses and reporting of the study data for use in the clinical study report (CSR). This SAP is being written with due consideration of the recommendations outlined in the most recent International Conference on Harmonisation (ICH) E9 Guideline entitled Guidance for Industry: Statistical Principles for Clinical Trials and the most recent ICH E3 Guideline, entitled Guidance for Industry: Structure and Content of Clinical Study Reports.

This SAP describes the analysis sets that will be analyzed, the subject characteristics parameters, the efficacy parameters, and the safety parameters that will be evaluated. The details of the specific statistical methods that will be used will be provided in this SAP. If differences occur between analyses described in the SAP and the current protocol, those found in this SAP will assume primacy. If additional analyses are required to supplement the planned analyses described in this SAP, they may be completed and will be identified in the CSR. Table and listing specifications are provided in a separate document.

## **2. PROTOCOL SUMMARY**

### **2.1 Study Objectives**

#### **2.1.1 Primary Objective**

The primary objectives of this study are to assess the safety and efficacy of MS1819 in enteric capsules vs porcine pancreatic enzyme replacement therapy (PERT) in patients with exocrine pancreatic insufficiency (EPI) due to cystic fibrosis (CF).

The primary safety objective of the study is to assess the safety and tolerability of doses of 2240 mg/day and 4480 mg/day of MS1819 provided in enteric capsules. The primary efficacy objective of the study is to assess the efficacy of MS1819 in enteric capsules vs. PERT.

#### **2.1.2 Secondary Objectives**

To evaluate and compare effects of MS1819 in enteric capsules and porcine PERT on other measures of digestion including the coefficient of nitrogen absorption (CNA), stool weight, body weight, body mass index (BMI), signs and symptoms of malabsorption, and serum liposoluble vitamins A, D, E, and K.

#### **2.1.3 Exploratory Objective**

The exploratory objective of the extension phase (EP) is to find a dose of MS1819 in immediate release capsules that is safe and results in CFA values in a therapeutic range.

### **2.2 Overall Study Design and Plan**

This is a Phase 2, open-label, multicenter, 2, 2x2 crossover study assessing the safety and efficacy of MS1819, 2240 mg/day vs porcine PERT, and 4480 mg/day vs porcine PERT given at the same dose and dosing regimen that was being administered during the pre-study period. MS1819 will be administered in enteric capsules.

MS1819 will be first assessed in a 2x2 crossover including approximately 30 patients completing both periods. Fifteen patients will be randomized to the MS1819 2240 mg/day vs PERT arm, and 15 patients will be randomized to the MS1819 4480 mg/day vs PERT arm. Patients in each arm will further be randomized to receive either the sequence consisting of MS1819 for 3 weeks followed by PERT for another 3 weeks or the opposite sequence of treatments, PERT for 3 weeks followed by MS1819 for another 3 weeks.

Randomized patients will be males or females, 18 years or older. Safety (adverse events [AEs], serious adverse events [SAEs], discontinuations due to adverse events, and safety laboratory values) will be assessed by descriptive methods. The primary efficacy endpoint is the coefficient of fat absorption (CFA) that will be assessed at the end of the 3-week period of treatment for each 2x2 crossover.

Patients enrolled into the extension phase (EP) will be composed of patients who have completed the crossover phase of OPTION 2. These patients must continue to comply

with the same inclusion and exclusion criteria as used in the crossover phase of the OPTION 2 trial (some screening tests may need to be repeated and all subjects must have completed an End of Study visit in the crossover phase).

Concomitant medications will be allowed as in the crossover phase. The Drug Product, immediate release capsules (MS1819 IR) each containing 140 mg of MS1819, will be the same as used in a previous OPTION trial (AZ-CF2001) of MS1819 in patients with EPI due to CF.

The EP will first enroll 9 patients, each receiving 4.4 grams/day of MS1819, for two weeks. At the end of 2 weeks, patients will enter confinement for a controlled diet, stool collection and CFA measurement. Data will be analyzed using descriptive statistics. Based upon resulting CFA and safety data, 5 additional patients may be enrolled at the 4.4 grams/day dose to better characterize the CFA following encouraging results from the initial 9 patients. If safety is satisfactory and the CFAs do not achieve values considered to be in the therapeutic range, 9 more patients will be enrolled and dosed at 6.7 grams/day for 2 weeks. These 9 patients may be patients who have participated in the 4.4 grams/day dose evaluation, as described above, or may be new patients from the OPTION 2 crossover phase. After treatment with MS1819 IR 6.7 grams/day for 2 weeks is completed, CFAs will be measured, and data assessed as before. Depending on safety and CFA analysis, either another 5 patients will be enrolled to better characterize encouraging initial results, or the study will be terminated.

Safety will be evaluated by the DMC Chairperson after the initial 9 patient phase of 4.4 grams/day, and again after the initial 9 patient phase of 6.7 grams/day, should that dose be studied.

A study flow chart is presented in Appendix 13.1 for the crossover phase and 13.2 for the extension phase, and a schedule of events is presented in Appendix 13.3 for the crossover phase and 13.4 for the extension phase.

### **2.3 Study Population**

Subjects that are  $\geq 18$  years of age with EPI due to CF will be enrolled. The inclusion and exclusion criteria for the study are enumerated in Sections 7.3.2 and 7.3.3 of the protocol, respectively.

### **2.4 Treatment Regimens**

At randomization for the crossover phase, subjects will be assigned in a 1:1:1:1 ratio to one of four arms:

- MS1819 (2240 mg/day) followed by prestudy porcine PERT
- Prestudy porcine PERT followed by MS1819 (2240 mg/day)
- MS1819 (4480 mg/day) followed by prestudy porcine PERT
- Prestudy porcine PERT followed by MS1819 (4480 mg/day)

MS1819 will be administered in enteric capsules for the crossover phase. Subjects will receive the same dose of PERT that was being administered during the prestudy period while in the porcine PERT period of their treatment sequence.

The extension phase will enroll patients as follows:

- 9 patients will be enrolled initially, each receiving 4.4 grams/day of MS1819 IR
- Based on resulting CFA data, 5 additional patients may be enrolled, each receiving 4.4 grams/day of MS1819 IR
- If safety in the 4.4 grams/day dose is found to be satisfactory and the CFAs do not achieve values in the therapeutic range, 9 patients will be enrolled, each receiving 6.7 grams/day of MS1819 IR
- Based on resulting CFA data, 5 additional patients may be enrolled, each receiving 6.7 grams/day of MS1819 IR

MS1819 will be administered in IR capsules for the extension phase.

## 2.5 Treatment Group Assignments or Randomization

Subjects who meet all of the enrollment criteria will be randomized to receive MS1819 (2240 mg/day) followed by PERT, PERT followed by MS1819 (2240 mg/day), MS1819 (4480 mg/day) followed by PERT, or PERT followed by MS1819 (4480 mg/day) using a 1:1:1:1 allocation ratio. MS1819 will be administered in enteric capsules.

The extension phase will include subjects that completed the crossover phase and will not be randomized. Subjects participating the extension phase will receive either the 4.4 grams/day or 6.7 grams/day dose of MS1819 IR capsules, depending on the part of the extension phase that subject is participating in, as detailed in the extension phase flow chart in Appendix [12.2](#).

## 2.6 Sample Size Determination

The primary objectives of this study are to assess the safety and efficacy of MS1819 in enteric capsules vs PERT in patients with EPI due to CF. The exploratory objective of the extension phase is to find a dose of MS1819 in immediate release capsules that is safe and results in CFA values in a therapeutic range. The sample size was selected to be sufficient to address the safety objectives of this trial.

Based upon CFA data obtained in the recently completed Phase 2a trial (OPTION), 15 patients per MS1819 dose should provide sufficient point estimates of CFA in each group in the crossover phase. Given the acceptable safety profile obtained in the OPTION trial a sample of 15 patients should be adequate for the observation of safety per dose of MS1819. This study will use descriptive analyses for both safety and efficacy analyses.

Likewise, in the EP, sample sizes are estimates based upon prior studies of similar design with CFA and safety endpoints.

### 3. GENERAL ANALYSIS AND REPORTING CONVENTIONS

The following is a list of general analysis and reporting conventions to be applied for this study.

Categorical variables will be summarized using counts (n) and percentages (%) and will be presented in the form “n (xx.x).” If a count is 0, 0% will be shown for the percentage. To ensure completeness, summaries for categorical and discrete variables will include all categories, even if no subjects had a response in a particular category.

Continuous variables will be summarized using mean, SD, minimum, maximum, median and number of subjects. The 25th and 75th percentiles will be provided for distributions that are known to be skewed. The mean, median, 25th percentile, 75th percentile, and confidence intervals (CI) will be reported to 1 more level of precision than the original observations, and the SD will be reported to 2 more levels of precision than the original observations. The minimum and maximum will be the same precision as the original data.

When p-values are provided, they will be rounded to 3 decimal places; p-values that round to “0.000” will be presented as “<0.001.” Unless otherwise stated, all statistical tests of treatment effects will be conducted at a 2-sided alpha level of 0.05.

All analysis will be performed using SAS® System version 9.3 or later.

Dates in listings will be displayed as yyyy-mm-dd (e.g., 2015-01-24).

Separate displays will be produced for each crossover phase dose (2240 mg/day, 4480 mg/day) and each extension phase dose (4.4 grams/day, 6.7 grams/day), unless otherwise stated.

For the crossover phase, in order to present summaries by treatment group regardless of sequence, the following parameters will be summarized as described below: safety laboratory, vital signs, signs and symptoms of malabsorption, weight, BMI, and serum liposoluble vitamins A, D, E, and K. These endpoints will be summarized relative to the time of first dose on a given study treatment. All post-randomization measurements will be relative to the time of the first dose. For example, in the MS1819 treatment column, the measurement at first dose will be Visit 3 if a subject is randomized to the MS1819-PERT sequence, and Visit 6 if a subject is randomized to the PERT-MS1819 sequence.

## 4. ANALYSIS POPULATIONS

The following 3 analysis populations will be identified for this study for each the crossover phase and the extension phase:

### 4.1 Modified Intent-to-Treat Population

The modified intent-to-treat (mITT) population for the crossover phase includes all randomized patients receiving at least one dose of treatment and having at least one valid stool collection and CFA post baseline while receiving their assigned study drug..

The mITT population for each stage of the extension phase includes all enrolled patients receiving at least one dose of treatment and having a valid stool collection and CFA during the relevant stage of the extension phase.

A stool sample will be considered valid if the date and time associated with the second blue dye marker is recorded, indicating that the stool sample collection is complete.

The mITT population will be used for efficacy analyses. Subjects will be analyzed according to the treatment group to which they were randomized for the crossover phase, regardless of the actual treatment received, unless stated otherwise.

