### 11.3 Extension Phase Study Design

This will be an open label, dose ranging study using an adaptive design. One and potentially two doses of immediate release MS1819 capsules will be studied. Given that we now have a large cohort of patients studied while using a stable dose of PERTs in OPTION and OPTION 2 we will not enroll further PERT control patients.

[figure not shown]
Patients enrolled into the extension phase (EP) will be composed of patients who have completed the crossover phase of OPTION 2. These patients must continue to comply with the same inclusion and exclusion criteria as used in the crossover phase of the OPTION 2 trial (some screening tests may need to be repeated and all subjects must have completed an End of Study visit in the crossover phase). Concomitant medications will be allowed as in the crossover phase. The Drug Product, immediate release capsules each containing 140 mg of MS1819, will be the same as used in a previous OPTION trial (AZ-CF2001) of MS1819 in patients with EPI due to CF.

The EP will first enroll 9 patients, each receiving 4.4 grams/day of immediate release capsules of MS1819, for 2 weeks. At the end of 2 weeks, patients will enter confinement for a controlled diet, stool collection and CFA measurement. Data will be analyzed using descriptive statistics. Based upon resulting CFA data, 5 additional patients may be enrolled at the 4.4 grams/day dose to better characterize the CFA following encouraging results from the initial 9 patients. If safety is satisfactory and the CFAs do not achieve values considered to be in the therapeutic range, 9 more patients will be enrolled and dosed at 6.7 grams/day for 2 weeks. These 9 patients may be patients who have participated in the 4.4 grams/day dose evaluation, as described above, or may be new patients from the OPTION 2 crossover phase. After treatment with 6.7 grams/day for 2 weeks is completed, CFAs will be measured, and data assessed as before. Depending on CFA analysis, either another 5 patients will be enrolled at the 6.7 grams/day dose to better characterize encouraging initial results, or the study will be terminated.

Safety will be evaluated by the DMC Chairperson after the initial 9 patient phase of 4.4 grams/day, and again after the initial 9 patient phase of 6.7 grams/day, should that dose be studied.

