**Table 3: Schedule of Assessments: Extension Phase**

	4.4 g/day TREATMENT PERIOD			6.7 g/day TREATMENT PERIOD			END OF EXTENSION STUDY/EARLY WITHDRAWAL TERMINATION
Visit Number	11 A	12(T) B	13 C	14 A	15 (T) B	16 C	17
Study Week	1	1	3	1	1	3	2 weeks after last dose of study drug
Study Days	E1	E5	E11	E1	E5	E11	
Visit Window (days)		±2	+4		±2	+4	±2
Pre-Visit Instructions		X			X		
Supervised confinement			X			X	
Clinical Assessments							
Obtain informed consent	X			X D			
Focused physical exam E	X		X	X		X	X
Height/weight, vital signs (sitting)	X		X	X		X	
Inclusion/exclusion criteria review	X			X D			
Concomitant medications	X	X	X	X	X	X	X
Adverse events	X	X	X	X	X	X	X
Confirm scheduled date for next supervised confinement visit	X	X		X	X		
Study Treatment							

Dispense study drug MS1819 (either 4.4 or 6.7g/day)	X			X			
Verify study drug count at the end of confinement			X			X	
Return MS1819 at the end of confinement			X			X	
Record fat and protein intake and study drug taken at all meals and snacks			X			X	
Efficacy Measures							
Malabsorption signs & symptoms	X	X	X	X	X	X	X
72-hour controlled diet record			X			X	
Marker-to-marker stool collection and stool weight F			X G			X G	
Laboratory Tests							
Pregnancy test (urine dipstick) H	X		X	X		X	X
Urinalysis			X			X	
Hematology, clinical chemistry, PT/INR, and aPTT I			X			X	
Fasting J lipids (patient to come in fasting status) and pre-albumin			X			X	
Serum samples for anti-LIP2 lipase antibodies and MS1819 concentrations	X		X	X		X	X
Diagnostic Tests							

Spirometry	X			X D			
Resume Prescribed PERT							
Switch back to prescribed porcine PERT F			X			X	

- A Subjects do not need to go through full screening again.
- B Visits 12, and 15 are telephone visits to assess any changes to AEs and concomitant medications in addition to confirming the visit date for the next scheduled supervised confinement.
- C Visits 13 and 16 are scheduled confinement visits and can take up to 7 days. A +4-day window is permitted around the scheduled confinement for both V13 and V16 to accommodate for scheduling. Dosing must have occurred for at least 10 days prior to the start of the scheduled confinement.
- D Only for patients that did not participate in first part of extension phase study

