##### **11.6.2 Missing Data**

Missing data will not be replaced.

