## 5. STUDY SUBJECTS

### 5.1 Disposition of Subjects

Disposition will be summarized separately for each dose of the crossover phase and each dose of the extension phase, unless stated otherwise.

The disposition of subjects will be summarized for all subjects screened in the study. The following disposition information will be summarized overall:

- The number of subjects screened.
- The number of subjects who failed screening and the reason for screen failure.

All percentages will use the number of screened subjects as the denominator.

The following disposition information will be summarized by treatment sequence for all subjects randomized in the study for the crossover phase:

- The number of subjects randomized.
- The number and percentage of subjects in the mITT population, PP population, and safety population.
- The number and percentage of subjects who completed the first treatment period (through Visit 6)
- The number and percentage of subjects who withdrew from the first treatment period and the reason for withdrawal
- The number and percentage of subjects who completed the second treatment period (through Visit 9)
- The number and percentage of subjects who withdrew from the second treatment period and the reason for withdrawal
- The number and percentage of subjects who completed the study (through Visit 10)
- The number and percentage of subjects who withdrew from the study and the reason for withdrawal

All percentages will use the number of randomized subjects as the denominator.

A data listing of subject disposition for all randomized subjects and a data listing of screen failures will also be provided for the crossover phase.

The following disposition information will be summarized for all subjects in the extension phase:

- The number and percentage of subjects in the mITT population, PP population, and safety population
- The number and percentage of subjects who were treated in the 2240 mg/day dose of the crossover phase

- The number and percentage of subjects who were treated in the 4480 mg/day dose of the crossover phase
- The number and percentage of subjects who were treated in both the 4.4 grams/day stage and the 6.7 grams/day stage of the extension phase
- The number and percentage of subjects who were treated in the 4.4 grams/day stage and not the 6.7 grams/day stage of the extension phase (4.4 grams/day summary only)

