- The number and percentage of subjects who were treated in the 6.7 grams/day stage and not the 4.4 grams/day stage of the extension phase (6.7 grams/day summary only)
- The number and percentage of subjects who completed the extension phase treatment period
- The number and percentage of subjects who withdrew from the extension phase treatment period
- The number and percentage of subjects who completed the extension phase of the study (through Visit 17)
- The number and percentage of subjects who withdrew from the extension phase of the study and the reason for withdrawal

All percentages will use the number of subjects enrolled in the extension phase as the denominator.

A data listing of subject disposition for all subjects enrolled in the extension phase and a data listing of screen failures will also be provided for the extension phase.

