#### **9.2.3.1 Coefficient of Fat Absorption**

The exploratory endpoint of CFA will be assessed at the end of the 2-week treatment period (Visit 13 for the 4.4 grams/day dose or Visit 16 for the 6.7 grams/day dose). CFA is evaluated by the 72-hour marker-to-marker stool sample collection (1 measure at Visit 13 and 1 at Visit 16) and standardized high-fat diet during each supervised confinement. CFA is collected and calculated as described in Section 9.2.1.

CFA at the end of the treatment period (Visit 13 or Visit 16) will be summarized for using descriptive statistics.

The descriptive summary of CFA at the end of the treatment period (Visit 13 or Visit 16) will also be provided using the per-protocol population.

In addition, CFA at the end of the extension treatment period (Visit 13 or Visit 16) will be compared against each the CFA at the end of the PERT crossover study period and CFA at the end of the MS1819 study period for the subset of subjects participating in the extension phase using descriptive statistics.

Fat consumed (g/24h), fat excreted (g/24h), and CFA (%) will be listed by visit for all subjects in the mITT population.

Details of each supervised confinement, including controlled diet and marker-to-marker stool collection, will be listed for all subjects in the mITT population.

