### **9.2.3.4 Signs and Symptoms of Malabsorption**

Signs and symptoms of malabsorption will be evaluated at Visits 11, 12, and 13 (4.4 grams/day) and Visits 14, 15, 16 (6.7 grams/day), as well as at Visit 17.

The EPI malabsorption symptoms will be evaluated as described in Section 9.2.2.3.

Stool frequency will be summarized for the mITT population using descriptive statistics.

The number and percentage of subjects within each category for stool consistency, bloating, abdominal pain, flatulence, incidence of visible oil/grease in stool, increased stool quantity, and worsening of overall bowel habit at each study visit will be summarized.

Signs and symptoms of malabsorption will be listed for all subjects in the mITT population.

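### Extension phase: no planned efficacy output counts a patient who stops before the V13 or V16 stool collection, so the reported CFA for a dose is likely to lean modestly upward

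*SAP*

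**What the plan says.** The extension phase looks for an immediate-release dose that is safe and brings CFA into a therapeutic range (Protocol 11.1). Nine patients receive 4.4 g/day for two weeks, and the next step depends on the result: "If safety is satisfactory and the CFAs do not achieve values considered to be in the therapeutic range, 9 more patients will be enrolled" (Protocol 11.3), at 6.7 g/day. Alternatively, five more may be added at 4.4 g/day if the first results are encouraging.

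The efficacy set for each stage is "all enrolled patients receiving at least one dose of treatment and having a valid stool collection and CFA during the relevant stage" (SAP 4.1). A collection is valid only if passage of the second dye marker is recorded. In Protocol Table 3, the row "Marker-to-marker stool collection and stool weight" is marked only at the V13 and V16 confinements; V17 has none. SAP 4.2 makes the per-protocol set a subset of mITT. Protocol 11.6.2 adds: "Missing data will not be replaced".

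The outputs follow that set. In SAP 9.2.3.1, "CFA (%) will be listed by visit for all subjects in the mITT population". In SAP 9.2.3.4, "Signs and symptoms of malabsorption will be listed for all subjects in the mITT population", and stool frequency is also summarised for mITT. The CFA summary and the categorical symptom summary name no set, so the general mITT rule of SAP 4.1 applies.

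**The concern.** A patient whose malabsorption worsens enough to stop before confinement is a treatment failure for that dose, but has no CFA and so leaves its efficacy set. Symptoms already recorded at V11/V12 or V14/V15 leave with that patient. What remains is a completers-only CFA.

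Two features make this more than a technicality. First, Protocol 5.6.3 reports five stops during MS1819 in OPTION, mainly for increased symptoms of pancreatic insufficiency, and the extension uses the same capsules. Second, under Protocol 9.1.1 worsening of the disease is not an adverse event unless it is serious. Adverse-event tables therefore need not show it, and SAP 8.1 names no safety output for the separate form on which it is recorded.

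At stake is whether the reported CFA makes a dose look closer to the therapeutic range than it is for all patients who start it.

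**Working it through.** The plan gives no power, SD or effect size for the extension, so there is no stated figure to reproduce. The check has three parts.

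**1. What one lost patient does to the mean of 9.** Suppose the 8 completers average 80%, the goal stated for the crossover in Protocol 5.7. The mean for all 9 is (8 × 80 + x)/9, where x is the unobserved CFA.
- x = 56 (OPTION mean on MS1819, Protocol 5.6.3): 696/9 = 77.3%.
- x = 7 (OPTION minimum on MS1819): 647/9 = 71.9%. This is an extreme case.

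**2. How often it happens and how far the mean moves.** Assumptions: CFA is 100 × a beta variable; n = 9; each patient with CFA below 50% stops with probability q; 400,000 simulated groups. The mean against 80% is an illustration only, because the plan states no rule.

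Loss per patient is q × P(CFA < 50). At mean 75 and SD 20, P(CFA < 50) = 0.132. With q = 0.25 the loss is 0.25 × 0.132 = 3.3%, and the chance of losing at least one of 9 is 1 − (1 − 0.033)^9 = 26%.

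| True mean, SD | P(mean ≥ 80), no loss | q = 0.25 | q = 0.5 |
|---|---|---|---|
| 75, 15 | 16% | 18% (shift +0.6) | 21% (shift +1.2) |
| 75, 20 | 24% | 30% (shift +1.3) | 37% (shift +2.7) |
| 75, 25 | 29% | 38% (shift +2.1) | 50% (shift +4.4) |
| 70, 20 | 6% | 9% | 13 to 14% |
| 65, 20 | 1% | 2% | 3% |

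At mean 75 and SD 20, q of 0.10 to 0.15 gives 26 to 27%, with a shift of +0.5 to +0.8 points.

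OPTION gives a rough guide to q. A beta with mean 56 and SD 15 to 25 puts 35 to 41% of patients below 50%, or about 11 to 15 of the 32 to 36 assumed to have been measured. If all five stops were below 50%, q = 5/(5 + 11 to 15), about 25 to 31%. The protocol says only that the stops were mainly for symptoms, and the extension is shorter and takes crossover completers. A quarter is therefore not a low guess, and a half is an upper case.

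**3. What an all-dosed count would show.** At mean 75 and SD 20, the true share with CFA of 80% or more is 49.5%. Completers alone show 49.5/(1 − 0.033) = 51% at q = 0.25 and 49.5/(1 − 0.066) = 53% at q = 0.5. Counting stoppers as not in range returns 49.5%, because in this model every stopper is below 80%.

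**The case against.** Four points can fairly be made against this.

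*Early stops are not hidden.* A reader might infer that such a patient disappears from the report. The documents do not support that. SAP 5.1 includes "The number and percentage of subjects who withdrew from the extension phase treatment period", and the same list tabulates withdrawal from the extension study with its reason. SAP 8.2 summarises time on treatment and lists first and last doses for every dosed patient. The treatment-period line does lack the reason that the crossover line carries ("The number and percentage of subjects who withdrew from the first treatment period and the reason for withdrawal"), but this matters only for a patient who stops drug and still completes V17. All of this stands. What is missing is an efficacy output that counts these patients. The comparison with crossover CFA in SAP 9.2.3.1 could show a stopper's earlier value, but no extension value.

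*The dose decision is not tied to the mITT mean.* A reader might infer that expansion or escalation rests on a biased mean. Neither document says so. The look is open-label in 9 patients, so a missing CFA would be known, and SAP 2.2 bases expansion on both CFA and safety data. The flow chart was not available for this review. This stands: the point concerns the reported CFA and the absence of a stated rule for early stops, not a demonstrated wrong decision.

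*The table and listing specifications are a separate document* and may include a listing of the disease form. That is possible and cannot be checked here.

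*The effect is small.* A shift of 1.3 points compares with a standard error of 20/√9 = 6.7 points, and the phase is exploratory and unpowered (Protocol 11.6.1, SAP 9.2.3). This also stands, and it limits the point to an inexpensive improvement.

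**Conclusion.** The point holds as a modest one. Under the stated rules the CFA reported for each extension dose is a completers' figure, and OPTION suggests that the missing patients would be those doing badly. The direction is therefore upward. In the illustrative case (true mean 75%, SD 20, a quarter of low-CFA patients stopping), the mean rises by about 1.3 points and the chance of a mean of 80% or more goes from 24% to 30%. With half stopping it is 37%. At a true mean of 65% or less, the chance of reaching 80% stays at a few per cent at most, so the effect on that threshold is negligible.

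Applying OPTION's rate directly (5 of 41, 12%) would give 1 − (1 − 0.122)^9 = 69% for losing at least one of 9. That should not be read together with the shift above: in the illustrative case the chance is 26%, and treatment here is shorter, in patients who completed the crossover.

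The size rests on the assumed SD, beta shape and stopping rule, and on using the 80% goal from Protocol 5.7 as the therapeutic range, which the extension does not define numerically. That mITT governs the CFA and categorical symptom summaries is read from the general rule in SAP 4.1.

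**What to change.** - **SAP 9.2.3.1.** Keep the unimputed mITT summary. Beside it give, for each dose, the number dosed and the number and percentage with CFA of 80% or more over all patients dosed at that dose (the extension safety population), with an exact 95% interval. Count a patient who stops before a valid collection as not in range, and list each stop reason. Show a patient still on drug whose collection was invalid in a separate row labelled missing.
- **Protocol 11.3 and SAP 2.4.** State that the expand or escalate decision considers this count beside the CFA summary.
- **Optional tidying.** Add the reason to the extension treatment-period withdrawal line in SAP 5.1. Align Protocol 7.3.4 (applied to the extension by 11.4.2), which places treated withdrawals in the mITT analysis, with the mITT definitions in Protocol 10.3 and SAP 4.1. SAP section 1 gives the SAP primacy, so this second change is one of wording only.

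The cost is a few sentences and some table rows; no new data are collected. There are two drawbacks. A stop for an unrelated reason counts as not in range, at 1/9 = 11 percentage points each, so the reasons must be shown. The interval is also wide: 5 of 9 gives 21 to 86%.
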